3.2.3 Adverse Events

In this SAP Part 2, treatment emergent AE (TEAE) will be defined for (a) the entire study, (b) the Randomized Treatment Period, and (c) the Extended Treatment Period.

TEAE in the Entire Study (TEAE)

TEAEs in the study are defined as new or worsening AEs that occurred in the window of first infusion and within 28 days of the last infusion of study drug, regardless of large gaps of treatment interruption.

TEAE in the Randomized Treatment Period (TEAE-R)

TEAEs during the randomized treatment period are defined as new or worsening AEs that occurred in the window of first dose of infusion of the blinded study drug (FG-3019 or placebo)

(Day 1) and within 28 days of the last infusion of FG-3019/placebo or before the first FG-3019 infusion in the extended treatment period, whichever occurs first.

TEAE in the Extended Treatment Period (TEAE-EX)

TEAEs-EX are defined as new or worsening AEs that occurred in the window of first infusion in Extension and within 28 days of the last infusion in Extension.

Below is an example of the three definitions of TEAE for multiple records of the same AE.

AE #	Period	Onset	AE	Severity	Serious-ness	Related to study drug?	TEAE	TEAE-R	TEAE-EX
1	Year 1	Screening	Headache	2	N	N	N	N	N
2	Year 1	Day 2	Headache	1	N	N	N	N	N
3	Year 1	Last Year 1 dose	Headache	2	N	Y	N	N	N
4	Year 1	10 days post last dose	Headache	3	Y	N	Y	Y	N
5	Year 1	45 days post last dose	Headache	4	Y	N	Y	Y	N
6	EX	Day 2-EX	Headache	2	N	Y	N	N	N
7	EX-2	Day 10 EX-2	Headache	1	N	N	N	N	N
Consolidated for Entire study summary			Headache	4	Y	Y	Y		
Consolidated for Year 1 summary			Headache	4	Y	Y		Y	
Consolidated for Extension summary			{none}	NA	NA	NA			N

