## 7 STUDY PROCEDURES-ALL COHORTS UNLESS OTHERWISE SPECIFIED

### 7.1 Study Procedures

The study procedures and assessments are presented for the Randomized Treatment phase in Appendix 1, for the Extended Treatment phase in [Appendix 2](#), and for End-of-Treatment and Follow-up periods in Appendix 3. See the Study Reference Manual for additional details.

The treatment period in the Randomized Treatment Phase begins on Day 1 (first infusion of Study Drug) and continues through Week 48. Visit windows are within  $\pm 3$  days of the scheduled visit date for Weeks 3 through 48.

After completion of Week 48 assessments and reporting of all AEs, subjects may be eligible to continue to open label treatment in the Extended Treatment Phase. All other subjects undergo the EOS assessments.

Eligible subjects from the Randomized Treatment Phase of the study are offered participation in the Extended Treatment Phase as described under Section [4.2.3](#) and illustrated in [Figure 1](#). A Transition Period of up to 3 weeks between the Week 48 Visit in the Randomized Treatment Phase and Day 1-EX in the Extended Treatment Phase is provided in order to determine subject eligibility for the Extended Treatment Phase and to arrange scheduling of the Day 1-EX Visit. The total interval between the Week 45 Visit in the Randomized Treatment Phase and the Day 1-EX Visit in the Extended Treatment Phase should not exceed 6 weeks. If necessary, an unscheduled visit should be performed to obtain repeat pulmonary function tests (FVC) if the interval between the Week 45 Visit in the Randomized Treatment Phase and the Day 1-EX Visit in the Extended Treatment Phase is expected to exceed 6 weeks.

The treatment period in the Extended Treatment Phase begins on Day 1-EX (first infusion of FG-3019) and continues until progression or withdrawal. Visit windows are within  $\pm 3$  days of the scheduled visit date.

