### 11.2 Definitions

#### 11.2.1 Definition of an Adverse Event (AE)

An AE can be any unfavorable and unintended sign (e.g., an abnormal and clinically significant laboratory finding), symptom, or disease temporally associated with the use of a drug, without any judgment about causality. This includes any occurrence that is new in onset or aggravated in severity or frequency from the baseline condition, or abnormal results of diagnostic procedures, including laboratory test abnormalities. An AE can arise from any use of the drug (e.g., off-label use, use in combination with another drug) and from any route of administration, formulation, or dose, including an overdose.

An AE includes medical conditions, signs, and symptoms not previously observed in the subject that emerge during the protocol-specified AE reporting period, including signs or symptoms associated with an underlying condition that were not present prior to the AE reporting period (Section 11.3.1).

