1 INTRODUCTION

The planned analyses for the Randomized Treatment Period are documented in Part 1 of the Statistical Analysis Plan (SAP) for study FGCL-3019-067: A Phase 2, Randomized, Double-Blind, Placebo-Controlled Study to Evaluate the Safety and Efficacy of FG 3019 in Patients with Idiopathic Pulmonary Fibrosis. This is the part 2 of the SAP, which documents the planned analyses for the Extended Treatment Period. This document is based on the protocol Amendment 5.0 dated 12DEC2016.

In this document, only new definitions and rules will be described; the same definitions and rules described in the Part 1 of the SAP will not be repeated.

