2.2 Assessments in Extended Treatment Period

- FVC and FEV1 are assessed at 12-week intervals.
- HRCT scan of the chest is performed at 24-week interval during extension period.
- SGRQ questionnaire is administered at 12-week intervals.
- Electrocardiogram (ECG) is assessed at 24-week intervals.
- Laboratory samples for safety assessments are collected at 6-week intervals.
- Serum and plasma samples for biomarker tests (including CTGF) are collected at 24-week intervals.
- Plasma samples for assessing HAHA are collected prior to dosing on Day 1 of Extension Period and at the End of Study (EOS) safety follow-up.
- Adverse events, concomitant medications, procedures, non-drug therapies, oxygen use are collected from signing ICF through End of Study (EOS).

- Vital signs are measured at every clinical visit. On dosing days, vital signs are measured at pre-, intra-, and post-infusion.
- Physical examination is performed at 6-week intervals.

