4.3 Definition of Baseline

For subjects who were randomized to FG-3019 arm, the original baseline defined in the Randomized Treatment Period as described in SAP Part 1 will be used. This definition will enable evaluation of long term treatment effect in safety and efficacy parameters.

For subjects who were randomized to placebo arm, baseline in Extension Period will be re-defined as last assessment prior to first dose in Extension on Day 1-EX. This will separate the effect of FG-3019 from placebo.

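### In SAP Part 2 section 3.2.3, the worked example flags AE #5 (onset 45 days after the last dose) as TEAE-R, but the written window closes by day 28

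*SAP*

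**What the plan says.** SAP Part 2, section 3.2.3, defines three kinds of treatment-emergent AE. All three require a new or worsening event.

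- **TEAE (entire study):** from the first infusion to 28 days after the last infusion of study drug, ignoring treatment gaps.
- **TEAE-R (Randomized Treatment Period):** from the first blinded infusion, ending "within 28 days of the last infusion of FG-3019/placebo or before the first FG-3019 infusion in the extended treatment period, whichever occurs first".
- **TEAE-EX (Extended Treatment Period):** from the first extension infusion to 28 days after the last one.

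A table then illustrates the three definitions with seven headache records from one subject. AE #5 is labelled Year 1, has onset "45 days post last dose", severity 4, serious Y, related N, and is flagged TEAE = Y, TEAE-R = Y, TEAE-EX = N. Three summary rows follow. The one labelled "Consolidated for Year 1 summary" shows severity 4, serious Y, related Y, TEAE-R = Y.

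Protocol 10.3.5 and 11.3.1 also use a window of 4 weeks after the last dose. The SAP Introduction says that "the same definitions and rules described in the Part 1 of the SAP will not be repeated"; Part 1 is not among the documents available for this review.

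**The concern.** The table is there to show how the definitions work, and on this record it shows the opposite of the text. Someone coding from the text would leave an event between day 28 and Day 1-EX out of the Year 1 TEAE summary; someone coding from the table would put it in.

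Such events can be in the database. Subjects who roll over stay under observation between their last blinded dose and Day 1-EX, and SAP 2.2 collects AEs through End of Study. At stake is whether a subject whose only event of a given kind falls in that gap counts as a Year 1 TEAE, and what worst grade is reported for a subject who has other events as well.

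**Working it through.** **Step 1: apply the written windows to the example.** The inputs are onset, severity and printed flags from the table in SAP 3.2.3. An event counts as worsening if its severity exceeds the screening severity of 2. TEAE-R also requires onset no later than the earlier of day 28 after the last blinded dose and the first extension infusion.

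| AE # | Onset | Severity | Printed TEAE / R / EX | By the text |
|---|---|---|---|---|
| 1 | Screening | 2 | N / N / N | N / N / N |
| 2 | Day 2 | 1 | N / N / N | N / N / N |
| 3 | Last Year 1 dose | 2 | N / N / N | N / N / N |
| 4 | 10 days after last dose | 3 | Y / Y / N | Y / Y / N |
| 5 | 45 days after last dose | 4 | Y / **Y** / N | Y / **N** / N |
| 6 | Day 2-EX | 2 | N / N / N | N / N / N |
| 7 | Day 10 EX-2 | 1 | N / N / N | N / N / N |

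The text reproduces 20 of 21 flags. The exception is AE #5 TEAE-R, because 45 > 28. Its TEAE = Y for the entire study is right: that definition ignores gaps, and the subject has later extension records.

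**Step 2: vary the assumptions.**

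- Worsening judged against the highest earlier severity: again 20 of 21, with the same single mismatch.
- Worsening judged against the immediately preceding record: 18 of 21, because AE #3 (severity 2 after 1) would also become Y on two flags. The example does not use that reference.
- TEAE-R window run to the first extension infusion, with either of the first two references: 21 of 21.

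So the conflict does not depend on how worsening is read, and only a longer window removes it.

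**Step 3: what follows for the Year 1 row.** It prints 4 / Y / Y (severity / serious / related).

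- TEAE-R = Y for the row stands through AE #4 (day 10, severity 3) whatever happens to AE #5.
- Severity 4 comes only from AE #5; the next highest Year 1 record is AE #4 at 3.
- Related = Y comes only from AE #3, which the table flags as not a TEAE.

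With AE #5 set to N, the row depends on which records feed it:

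| Records used | Year 1 row |
|---|---|
| All records labelled Year 1 | 4 / Y / Y (as printed) |
| Records inside the TEAE-R window | 3 / Y / Y |
| Records flagged TEAE-R only | 3 / Y / N |

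Taking the worst value over all records in the labelled period, once any record is flagged, reproduces all 9 printed cells (3 rows × 3) both before and after the correction. Part 2 does not state that rule.

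**Step 4: how wide is the gap?** Let d be the days from the last blinded dose to Day 1-EX. Onset days where text and example differ run from 29 to d − 1, so their number is max(0, d − 29). Protocol 7.1 says the interval from the Week 45 visit to the "Day 1-EX Visit in the Extended Treatment Phase should not exceed 6 weeks", that is 42 days.

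- d ≤ 29: 0 days.
- d = 42 (Week 45 dose, at the limit): 42 − 29 = 13 days, onset days 29 to 41.
- d = 63 (Week 45 dose missed, last dose at Week 42): 63 − 29 = 34 days.

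AE #5's own day 45 lies beyond 42, so the example presumes a last dose before Week 45 or an interval longer than the protocol's limit.

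**The case against.** **The cell may be right and the text wrong.** A window to the first extension infusion matches every flag, and the printed Year 1 severity of 4 agrees with the flag. The protocol's 4 weeks is a general TEAE window, not a rule written for TEAE-R. This stands in part: the documents do not show which version was intended. It bears on the direction of the repair, not on whether one is needed.

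**The last infusion might mean the last one in the whole study.** That would give Y for AE #5. But the sentence defines the randomized period, and the drug pair it names repeats the blinded study drug. If this was meant, the text still needs rewording.

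**The effect is small.** This stands. SAP section 4 plans no formal inference, SAP 3.2.5 reports percentages of subjects, and the example headache remains a Year 1 TEAE through AE #4. For subjects who do not roll over, protocol 11.3.1 ends AE collection 4 weeks after the last dose, so the gap concerns rollovers.

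A reader might go further and infer three things that the documents do not support:

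- **That related = Y in the Year 1 and entire-study rows is a second error.** It does draw on records flagged as non-TEAE, but it breaches no stated rule, and one simple rule reproduces every printed cell.
- **That the plan has no consolidation rule.** Only Part 2 lacks one. Part 1 may hold it, and Part 2 says that it does not repeat Part 1. Nor is there a basis for preferring a flagged-records-only rule, which fits the printed rows worst (7 of 9 cells, 6 of 9 after the correction).
- **That TEAE-EX is undefined for placebo crossovers because 3.2.3 does not cite SAP 4.3.** Section 4.3 already resets their extension baseline. A missing pointer is editorial.

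**Conclusion.** Wrong as written, and minor. The TEAE-R flag of AE #5 contradicts the definition it is meant to illustrate; it is 1 flag of 21. The written definition, with support from the protocol's 4-week window, gives N.

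The consequence is confined to descriptive TEAE summaries for events with onset from day 29 up to the day before Day 1-EX. That is 0 to 13 onset days when the last blinded dose is at Week 45 and the 6-week limit is kept, and more only with a missed dose or a longer interval. The documents give no count of such events, so none is claimed. In the example itself only the Year 1 severity (4 or 3) and relatedness (Y or N) could change, depending on the consolidation rule.

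The conclusion assumes that the last infusion in the TEAE-R sentence is the last blinded one, and that worsening is judged against screening or the highest earlier severity. Part 1 could settle the consolidation rule, but it cannot remove a contradiction printed within Part 2.

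**What to change.** 1. Set AE #5 to TEAE-R = N and leave its entire-study TEAE = Y. If the sponsor intended the Year 1 window to run to the first extension infusion, keep the flag and amend the TEAE-R definition instead. Either way, text and table should agree with each other and with SAP Part 1.
2. In the same edit, re-check the consolidated Year 1 row. Confirm against SAP Part 1 which records feed the consolidated rows, then keep or change the severity of 4 accordingly. TEAE-R = Y for the row stays.

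The cost is small and no new data are needed. Amending the definition changes one sentence and no cells. Correcting the flag changes one cell, plus the Year 1 severity, and possibly relatedness cells, if the rule in Part 1 restricts which records count.

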3.2.4 Patient-Exposure-Years

Patient-Exposure-Years (PEY) is defined as the sum of all subjects' duration of follow-up in years, on FG-3019 or placebo respectively, for the entire study. A subject's duration of follow-up is defined as time from the first dose to the last follow-up recorded in the database. For those

who died, their date of death is the date of last follow-up. For subjects who are randomized to placebo and treated in extension, their last follow-up on placebo is defined as the date prior to Day 1-EX. For other subjects, date recorded on End-of-Study Disposition is the date of last follow-up.

3.2.5 TEAE and Mortality

TEAE and mortality will be reported in percentage per total number of subjects exposed.

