**Figure 1. Study Schema**

#### 4.2.2 Randomized Treatment Phase

Treatment should begin within 42 days of the first screening visit. Study Drug (FG-3019 [30 mg/kg] or placebo) will be administered by IV infusion every 3 weeks for a total of 16 infusions over 48 weeks.

The schedule of assessments of safety and efficacy are provided in Appendix 1 and Appendix 2. Safety and tolerability will be monitored closely by FibroGen. Cumulative safety experience will be evaluated by FibroGen on a regular basis. Final efficacy assessment is in Week 48. Subjects who do not enter the Extended Treatment Phase will undergo end-of-study (EOS) assessment (Appendix 3) on Week 49 (4 weeks after last dose of study drug).

After all subjects complete Week 48 evaluations or prematurely discontinue the study, data will be cleaned and locked for the primary analysis of efficacy and safety.

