4 GENERAL STATISTICAL CONSIDERATIONS

Efficacy and safety data will be summarized descriptive for subjects who entered extension and for all subjects who have been treated in the study. No formal statistical inference will be performed.

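### SAP Part 2 defines patient-exposure-years but never uses them, so whole-study TEAE and death percentages by treatment received are not comparable and may overstate FG-3019 risk

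*SAP*

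**What the plan says.** SAP Part 2 section 3.2.4 reads: "Patient-Exposure-Years (PEY) is defined as the sum of all subjects' duration of follow-up in years, on FG-3019 or placebo respectively, for the entire study". Each subject's follow-up is the "time from the first dose to the last follow-up recorded in the database". It ends at death or at the date on the End-of-Study Disposition page. For placebo subjects who go into the extension, "their last follow-up on placebo is defined as the date prior to Day 1-EX".

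Section 3.2.5 then fixes the reporting measure: "TEAE and mortality will be reported in percentage per total number of subjects exposed". Sections 5.5 (exposure) and 5.7.1 (TEAEs and mortality) mention no rate, and PEY does not appear again in Part 2.

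On who is summarized, the text is not uniform:
- Section 4 covers efficacy and safety data "for subjects who entered extension and for all subjects who have been treated in the study", descriptively and without formal inference.
- The heading of section 5.7 names both the Extension Period and the Overall Study.
- Section 5.7.1 itself mentions only subjects who entered the extension.
- Protocol section 10.3.1 groups safety data by actual treatment received.

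Section 3.2.3 defines TEAEs for three windows: the entire study, the randomized period (TEAE-R) and the extension (TEAE-EX). The entire-study window runs from the first infusion to "within 28 days of the last infusion of study drug, regardless of large gaps of treatment interruption".

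**The concern.** The percentage of subjects with at least one event rises with time at risk, and the design gives the two treatments unequal time. Randomized treatment is "every 3 weeks for a total of 16 infusions over 48 weeks", and the gap before Day 1-EX may be up to 3 weeks (Protocol 7.1). FG-3019 in the extension continues until FVC stopping criteria are met (Protocol Appendix 2, note a). A whole-study table by treatment received would therefore set a placebo group of about one year beside an FG-3019 group that mixes short and long exposure. A reader could not tell how much of a difference in TEAEs or deaths comes from the drug and how much from time.

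PEY is the natural remedy and is already defined, but it would not work as written for TEAEs. It counts time to the disposition date, whereas TEAEs stop 28 days after the last infusion. It is also not cut at a subject's first event.

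**Working it through.** The plan states no TEAE rate, death rate or PEY total, so there is no figure of its own to reproduce. The check asks what crude percentages would show if the drug had no effect on event rates.

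**Inputs from the documents**
- Last randomized dose at Week 45 (Protocol Appendix 1). A window of 28 days (4 weeks) then gives 45 + 4 = 49 weeks.
- FG-3019 mean change in FVC % predicted at Week 48 of −2.8, SD 7.3, dropout 10% (Protocol 10.1).
- Arm A subjects enrolled under the amendments continue only if FVC % predicted is above the original baseline (SAP 2.1).

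**Assumptions (not in the documents)**
- The same constant hazard h on both treatments. I use 0.10, 0.13 and 1.0 per person-year. The 0.13 is the population exacerbation rate in Protocol 1.1, borrowed only as an illustration.
- 48 or 96 extra weeks for those who continue. Everyone else is given 49 weeks.
- Normally distributed FVC change.

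**Step 1. Share of Arm A that continues.** P(change > 0) = 1 − Φ(2.8/7.3) = 0.351. Times 0.90 completers = 0.316, about 32%. Under the original protocol's rule (decline of less than 3), P = 1 − Φ(−0.2/7.3) = 0.511 of completers.

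**Step 2. Crude percentage for one subject.** p(t) = 1 − exp(−h·t/52), with t in weeks.

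| h per year | 49 weeks | 97 weeks | 145 weeks |
|---|---|---|---|
| 0.13 | 11.5% | 21.5% | 30.4% |
| 1.0 | 61.0% | 84.5% | 93.8% |

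**Step 3. Group percentage on FG-3019.** 0.68·p(49) + 0.32·p(49 + extra), with crossovers following the same pattern, so the share who cross over does not matter.
- h = 0.13, 48 extra weeks: 0.68 × 11.53 + 0.32 × 21.53 = 14.7% v 11.5%, ratio 1.28.
- h = 0.13, 96 extra weeks: 0.68 × 11.53 + 0.32 × 30.41 = 17.6% v 11.5%, ratio 1.52.
- h = 1.0: 68.5% and 71.5% v 61.0%, ratios 1.12 and 1.17.

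**Step 4. Can the sign reverse?** Take 68 subjects per arm (136/2). Let 90% of placebo subjects (61.2) cross over with an average of x weeks on FG-3019, and give Arm A continuers 48 extra weeks. At h = 0.10, Arm A shows 11.6% and placebo 9.0%.
- x = 24 weeks: (68 × 11.56 + 61.2 × 4.51)/129.2 = 8.2%, ratio 0.91.
- x = 36 weeks: ratio 1.03.
- x = 49 weeks: 10.3%, ratio 1.15.

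**Step 5. TEAE-R.** The window is about 49 weeks in both arms, so the ratio at equal hazards is 1.0.

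**Step 6. Would PEY as defined repair it?** For deaths, yes: follow-up already ends at death, so equal hazards give equal rates. For first TEAEs, no. Dividing subjects with an event by total follow-up at h = 1.0 gives 0.610/0.942 = 64.8 per 100 PEY at 49 weeks, but 0.845/1.865 = 45.3 at 97 weeks. The longer-followed group would look falsely safer. If time is cut at the first event, expected time is p/h, so the rate returns h in both groups.

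**The case against.** The strongest case against is that the problematic table may not be planned. Section 5.7.1 refers only to subjects who entered the extension, all of whom receive FG-3019, and sections 4.5 and 5.7.2 are limited in the same way. That limits the point, but does not remove it. Section 4, the 5.7 heading, the entire-study TEAE definition and Protocol 10.3.1 together put whole-study summaries by treatment received in scope, and a PEY split by treatment has little purpose otherwise.

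TEAE-R is a time-matched comparison. This stands in full: for randomized-period TEAEs, a true excess can be separated from longer exposure. It does not repair the entire-study percentages, and 3.2.5 gives mortality no matched period.

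Part 1 of the SAP is not among the documents, so exposure-adjusted rates for the randomized period cannot be ruled out. Part 2 says that it describes only new definitions, however, and PEY is defined here for the entire study.

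The summaries are descriptive. That is true, but readers still judge safety from descriptive death and TEAE tables.

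A reader might also take section 3.2.4 literally and start crossover FG-3019 time at the first placebo dose. The split by treatment and the placebo cut-off before Day 1-EX show that this is not intended. The wording only needs an explicit start date.

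**Conclusion.** The point holds in a limited form. PEY is defined and left unused in Part 2, and whole-study crude percentages by treatment received would not be comparable. Under equal hazards, with about 32% of Arm A continuing for 48 or 96 extra weeks and crossovers alike, the apparent ratio is about 1.28 to 1.52 at 0.13 per year and 1.12 to 1.17 at 1.0 per year. With short crossover exposure it can drop to about 0.91 at 0.10 per year. Hazards, extension lengths and crossover exposure are assumptions. A constant hazard is itself doubtful, because Arm A subjects pass an FVC screen before continuing.

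A reader might infer that FG-3019 is bound to look worse, or that its risk would appear to double or nearly triple. The documents support neither. The direction depends on crossover exposure, and a doubling or more needs nearly every FG-3019 subject to be followed for two or three years. The randomized-period TEAE comparison and the primary efficacy result are unaffected.

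**What to change.** In SAP 3.2.5 and 5.7.1, keep the percentages and add rates per 100 patient-years with 95% CI, for FG-3019 and for placebo, in all treated subjects.

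- **TEAEs:** count subjects with a first event. End each subject's time at the first event or the end of the TEAE window, whichever is earlier.
- **Deaths:** end time at death or last known vital status. Use all treated subjects, because placebo deaths among extension entrants are zero by construction (they had to survive to Day 1-EX), and no denominator corrects that.
- **Section 3.2.4:** state that FG-3019 time for crossovers starts at Day 1-EX, and name the tables that use PEY.
- **Between-arm TEAE comparison:** base it on TEAE-R, and say that entire-study percentages are not to be compared across treatments.
- **Section 5.7.1:** reconcile its population with section 4 and the 5.7 heading.

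The cost is SAP wording and a few extra table columns. The infusion, event, death and disposition dates are already needed for the existing definitions.
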